6.8 Description of Treatment and Definition of Exposure to Trial Medication

Treatment is defined as the process of embryo culture and assessment, whereas no trial medication is applied in this trial.

In the experimental treatment arm:

- On Day 1 of embryo culture, all 2PN zygotes are transferred by embryologists into the GERI dishes which have been pre-equilibrated. The GERI dishes are then placed in the GERI+ incubator for both bright-field and dark-field time lapse monitoring until Day 3. Pre-mixed Gas with 6% CO₂ (or whichever CO₂ concentration is required to meet manufacturers requirements for optimal pH of their culture media) and 5% O₂ is recommended.
- . If a different gas composition is used, this must be the same for both test and control arms.
- On Day 3 of embryo culture, all embryos are reviewed firstly by GERI Assess software, using bright-field imaging. Five parameters, including cell number, abnormal divisions (reverse cleavage and direct cleavage), multinucleation, fragmentation and symmetry of blastomeres are annotated in the GERI Assess system.
- It is recommended that Day 3 cell count is assessed at 68±1 hours post-insemination across all sites, for generation of final EEVA score (Alpha Scientists in Reproductive Medicine and ESHRE Special Interest Group Embryology, 2011).
- The prognostic EEVA information, used adjunctively with morphology assessment will assist embryologists to further identify, for transfer, the embryo(s) with optimal potential to form a blastocyst.
- Finally, the embryo(s) with the highest EEVA grade are transferred. **Note:**

Protocol Version: 3.0 / Jan 31, 2018 22 / 49

trial

Cell number should be entered via the EEVA system, to generate a final EEVA test result (based on the dark-field imaging). A second review of embryo videos should be carried out to confirm P2 and P3 parameters, and when required, a manual update should be carried out.

- EEVA results should be applied only to those embryos of overall good and fair quality i.e. ≥ 6 cells with ≤ 25% fragmentation and without severe asymmetry. EEVA test results are not recommended for adjunctive use with poor quality embryos i.e. ≤ 5 cells or 6 cells with > 25% fragmentation and with severe asymmetry.
- Priority should be given to transfer embryos without direct cleavage or reverse cleavage.
- If the EEVA result shows "NR" (No Result) or there are only poor-quality embryos, the embryologist will grade the embryos with morphology (Alpha Scientists in Reproductive Medicine and ESHRE Special Interest Group Embryology, 2011) and apply the decision grid used in the control group.
- If two or more embryos have the same EEVA score, preference should be given to the embryos with better morphology and subject to the embryologist's decision grid used in the control group.
- National/regional regulations and procedures will be followed to manage the remaining embryos, provided that in each case the provisions of the Germany Embryo Protection Act are observed.

In the control treatment arm:

- On Day 1 of embryo culture, all 2PN zygotes are transferred by embryologists into the GERI dishes which have been pre-equilibrated with embryo culture medium routinely used in their laboratory. The GERI dishes are then placed in a conventional incubator for culture until Day 3. Gas with 6% CO₂ (or whichever CO₂ concentration is required to meet manufacturers requirements for optimal pH of their culture media) and 5% O₂ is recommended. If a different gas composition is used, this must be the same for both test and control arms.
- On Day 2 of embryo culture, the embryos may or may not be taken out of the incubators for observation using bench-top microscopy, to follow the routine protocols of the laboratory.

Protocol Version: 3.0 / Jan 31, 2018 23 / 49

trial

• On Day 3 of embryo culture, all embryos are assessed using a bench-top microscope by embryologists, at a recommended time of 68±1 hours post insemination. (Alpha Scientists in Reproductive Medicine and ESHRE Special Interest Group Embryology, 2011). The embryo(s) with optimal cell stage and grade will be transferred. National/regional regulations and procedures will be followed to manage the remaining embryos, provided that in each case the provisions of the Germany Embryo Protection Act are observed.

Please be advised that there is no restriction on the number of embryos to be transferred but we recommend a single embryo transfer in this study.

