#### Per Protocol (PP) dataset:

(PP) dataset is defined as:

Subjects, who completed the study without major protocol deviation, and:

- For subject randomized Geri+ group:
  - o embryos are cultured to Day 3, and are assessed by Eeva per Eeva IFU, or by standard morphology if this subject only has poor quality embryos;
  - embryo(s) with the highest Eeva score (for subjects with good and fair quality embryos), or best morphology grade (for subjects with poor quality embryos only, or with poor quality embryos and no more than one good/fair quality embryos) is/are transferred on Day 3 of embryo culture;
- For subjected randomized to Control group:
  - Embryos are cultured to Day 3, and the embryo(s) with the optimal cell number and grade is/are transferred.

Major protocol deviations are defined in section 8.1

The FA population is the primary analysis population.

PP population is used for sensitivity analysis. PP population will be considered only if it is less than 90% of FA population and more than 40% of total planned number of subjects.

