#### **Eeva conformity:**

The qualitative variables

- Eeva conformed subjects
- Eeva non-conformed subjects

will be summarized by using number and percentage for GERI+ Incubator treatment group from (FA) dataset.

Eeva conformed subjects: embryo transfer is based on Eeva result applied to good and fair quality embryos.

Eeva non-conformed subjects: embryo transfer is not based on Eeva result (when either of the boxes in the last two columns of eCRF CP6 is ticked).

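### A GERI+ woman whose site follows the protocol's abnormal-cleavage sentence can be excluded from the SAP's Per Protocol set

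*Protocol*

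**What the plan says.** **Protocol 6.8, GERI+ arm.** Embryos are first reviewed in GERI Assess on bright-field images, where "abnormal divisions (reverse cleavage and direct cleavage), multinucleation, fragmentation and symmetry of blastomeres are annotated in the GERI Assess system". An EEVA result, based on dark-field imaging, is then produced. The sequence closes with: "Finally, the embryo(s) with the highest EEVA grade are transferred". Notes follow. One restricts EEVA to embryos of good or fair quality, judged on cell number, fragmentation and symmetry. Another reads: "Priority should be given to transfer embryos without direct cleavage or reverse cleavage". Further notes deal with a missing EEVA result, with women who have only poor embryos, and with ties: "If two or more embryos have the same EEVA score, preference should be given to the embryos with better morphology".

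**SAP 8.2, PP set.** The definition opens with "Subjects, who completed the study without major protocol deviation, and" and then adds conditions by arm. In the GERI+ arm the transfer must be of "embryo(s) with the highest Eeva score (for subjects with good and fair quality embryos), or best morphology grade". The morphology alternative is reserved for women with poor embryos only, or with poor embryos and at most one good or fair embryo. In the control arm the embryo(s) with optimal cell number and grade must be transferred.

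**Related text.** SAP 8.1 lists five major deviations and calls all others minor. Protocol 8.3 defines PP more broadly: treated according to the protocol, Day 3 fresh transfer, and no major violation likely to affect efficacy. SAP 13 counts a GERI+ woman as Eeva non-conformed where "embryo transfer is not based on Eeva result", as shown by boxes in the last two columns of an eCRF page.

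**The concern.** Choosing the embryo is part of the experimental treatment, so the rule for choosing it should be clear, and the analysis set meant to capture adherence should follow that rule. Here one foreseeable case is not settled in the protocol, and the SAP decides it one way without saying so.

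What is at stake is the PP sensitivity analysis. A GERI+ woman can be classed as not per protocol because of an embryo feature seen after randomization, although her site did what a protocol sentence asked. The women concerned are a selected group: those whose top-graded embryo divided abnormally. Protocol section 3 describes such divisions as marks of poor embryo quality, so the group cannot be assumed to have the same prognosis as the rest.

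**Working it through.** **Step 1. When do the two sentences point to different embryos?** Take a woman with two embryos that are both good or fair.

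| | Embryo A | Embryo B |
|---|---|---|
| EEVA grade | highest | lower |
| Direct or reverse cleavage | yes | no |
| Chosen by the EEVA sentence | yes | no |
| Chosen by the cleavage note | no | yes |

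If the top-graded embryo is free of abnormal cleavage, or no clean alternative exists, there is no conflict.

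**Step 2. Does other text in 6.8 settle this case?**
- The quality restriction does not. Good or fair status does not use cleavage pattern, so embryo A can be eligible for EEVA and hold the top grade.
- The tie rule does not. The grades differ here, and that rule turns on morphology without naming cleavage.
- The notes on a missing EEVA result and on poor embryos only do not apply.
- Nothing says that the EEVA grade already screens out abnormal cleavage. Cleavage is annotated separately, on different images.

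**Step 3. How does the SAP classify a transfer of embryo B?** The woman has two good or fair embryos, so she is outside the morphology branch and the highest score is required. The transfer is not one of the five major deviations in SAP 8.1, but the score condition applies in addition to having none. She is therefore out of PP. Protocol 8.3 could keep her, and SAP 7 does not list this as a change from the protocol. If embryo A is transferred instead, she stays in PP, even on the reading that the note takes precedence.

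**Step 4. The plan's own numbers.** Inputs from Protocol 8.1: 30% versus 30% × 1.25 = 37.5%, two-sided alpha 0.05, power 80%, drop-out 10%. The mean rate is 0.3375.

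n = [1.960 × √(2 × 0.3375 × 0.6625) + 0.8416 × √(0.30 × 0.70 + 0.375 × 0.625)]² / 0.075² = 622.8, so 623 per group. Then 623 / 0.90 = 692.2, so 693 per group and 1,386 in all. The stated figures reproduce, and this point does not affect them.

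**Step 5. Upper bound on women dropped.** The frequency is not in the documents, so it is assumed: 5%, 10% or 20% of 693.
- 0.05 × 693 = 34.65, about 35
- 0.10 × 693 = 69.3, about 69
- 0.20 × 693 = 138.6, about 139

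**Step 6. Would PP be used?** SAP 8.2 uses PP only if it is below 90% of the full analysis set (0.90 × 1,386 = 1,247.4) and above 40% of planned subjects (0.40 × 1,386 = 554.4). With the planned drop-out, 2 × 623 = 1,246 complete, which is already below 1,247.4. Removing 5%, 10% or 20% of 623 GERI+ completers leaves 1,246 − 31 = 1,215, 1,246 − 62 = 1,184 or 1,246 − 125 = 1,121. All are above 554.4, so on the plan's own assumptions PP would be used.

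**Step 7. How far could the GERI+ PP rate move?** Let f be the fraction dropped among GERI+ women otherwise in PP, R the pregnancy rate in all of them, and r the rate in those dropped. Then

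PP rate − R = (R − f·r)/(1 − f) − R = [f/(1 − f)] × (R − r).

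The multiplier is 0.05/0.95 = 0.053, 0.10/0.90 = 0.111 or 0.20/0.80 = 0.25. Each percentage point of difference between R and r moves the GERI+ rate by about 0.05, 0.11 or 0.25 points. The documents give neither the size nor the sign of R − r.

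**The case against.** The strongest reply is that 6.8 is coherent. It describes a sequence, and the cleavage sentence stands among notes of which several plainly qualify the closing EEVA instruction. Priority is itself a word of order. EEVA is also described as adjunctive to morphology, so some embryologist judgement belongs to the intervention. This reading is natural, though the protocol does not state it. It does not rescue the SAP: if the note qualifies the EEVA sentence, SAP 8.2 excludes women treated as the protocol intends.

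A reader might also infer more than the documents support:
- **That only the GERI+ arm loses women over embryo selection.** This is wrong. SAP 8.1 makes failure to transfer the optimal control embryo a major deviation, and SAP 8.2 repeats the condition. The difference is that the control condition matches the control instruction in 6.8.
- **That sites applied two strategies under one label.** This cannot be shown. Protocol 10.8 mentions a GERI Assess/EEVA decision tree as a training topic, and SAP 8.2 refers to the Eeva instructions for use. Neither is in the documents, and either may fix the order.
- **That the Eeva conformity figure understates adherence.** It may, but this depends on eCRF boxes not shown. Choosing the best EEVA grade among embryos without abnormal cleavage could still count as based on EEVA.

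It also stands that the effect is confined. The full analysis set keeps these women, and SAP 7 plans no between-group comparison or confidence interval.

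**Conclusion.** The point holds as a mismatch between Protocol 6.8 and SAP 8.2. The protocol leaves one selection case unsettled. The SAP's PP rule can class as non-adherent a GERI+ woman whose site followed a protocol sentence, on a feature observed after randomization. That can distort the PP comparison; the direction and size are unknown.

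The count of about 35 to 139 women is a ceiling under an assumed 5% to 20%, not an estimate. It takes all 693 randomized women as the base, including those with no transfer or in the morphology branch, and it assumes that every affected site acted on the cleavage note. Because PP is a conditional, descriptive sensitivity set, the matter is one of clear definition and interpretation. It does not threaten the primary analysis set.

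**What to change.** The sponsor should reconcile the two sentences in Protocol 6.8 into one stated order, consistent with the decision tree used in training. SAP 8.2 and the Eeva conformity definition in SAP 13 should then be aligned, so that a transfer made as the protocol asks counts as adherent. Which rule prevails is for the sponsor to decide.

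Timing matters. SAP version 2.0 is dated 14 January 2020, and the protocol planned the last patient in for December 2019. On that calendar a change to 6.8 would not alter treatment already given. If treatment is complete, the SAP should count as adherent for PP a transfer made under either sentence, and tabulate those cases by site.

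The cost is one protocol clarification and two SAP sentences. The tabulation depends on access to the GERI Assess annotations, since the eCRF items listed in Protocol 7.3 do not name cleavage pattern. If the annotations cannot be retrieved, the report should say that these women cannot be separated from other departures from the highest score.

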6.9 Criteria for Subject Withdrawal

Subjects will be informed that they have the right to withdraw from the trial at any time between randomization and completion of the study, without prejudice to their medical care, and that they are not obligated to state their reasons. Any withdrawal must be fully documented in the source documents, including the reason for withdrawal.

Subject data will be included in the analyses up to the time that consent is withdrawn. The trial exit electronic case report form should be completed at the time a subject is withdrawn from the trial and will included the reason for withdrawal.

6.10 Definition of Completion of the Study

Completion of the study is achieved when all subjects finish the test for ongoing pregnancy.

The subject may complete and exit from this trial at the following time points:

- Test for hCG 12-18 days post embryo transfer: a subject will exit from the trial if the blood or urinary test result for hCG is negative. Otherwise subject waits until the test for clinical pregnancy.
- Test for clinical pregnancy at gestational weeks 6-8: a subject will exit from the trial if the ultrasound test result for clinical pregnancy is negative. Otherwise the subject waits until the test for ongoing pregnancy.
- Test for ongoing pregnancy at gestational weeks 10-12: a subject will finish the

Protocol Version: 3.0 / Jan 31, 2018 24 / 49

trial

trial at this time point, regardless of whether the ultrasound result for ongoing pregnancy is positive or negative.

 Miscarriage: a subject will exit from the trial upon spontaneous or therapeutic miscarriage.

6.11 Potential Confounding Factors

Smoking status, age, gestational history, COS strategy, embryo culture media, luteal phase support, number of embryos transferred and site locations are potential confounding factors in this study. Multivariate logistic analysis will be performed with these factors in the model as covariates when testing the primary endpoint.

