8. STATISTICS

8.1 Sample Size

Based on an expected clinical pregnancy rate of 30% (Adamson et al., 2016) in the control group and a 25% relative increase of clinical pregnancy rate in the experimental group, a two-sided test with an alpha level of 0.05 needs 623 subjects per group to reach a power of 80%. With a drop-out rate of 10%, 1,386 subjects (693 per group) need to be randomized. A subject can be considered as a drop-out during the study if she is randomized but primary endpoint data is not available for this subject, for whatever reason.

The calculation of sample sizes was performed using nQuery Advisor® version 7.0.

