8.4.2 Analysis of Primary Endpoint

The FHB positive clinical pregnancy rate (the number of subjects with FHB positive clinical pregnancy divided by the number of subjects with embryo transfer) for either of the two treatment groups will be computed.

Primary hypothesis will be tested between the treatment groups based on a Cochrane-Mantel-Haenzel CMH test adjusting for stratification factors providing the derived Odds Ratio and its 95% confidence interval. As sensitivity analysis, a logistic regression model with confounding factors and stratification factors as covariates will be performed. Details regarding the model and analysis will be specified in the SAP.

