# 7 Changes to the Planned Analyses in the Clinical Trial Protocol

The statistical methods as described in the protocol were adopted and no changes to the planned analyses. However Statistical comparison between groups and confidence intervals will not be performed. No regression models will be constructed in this study.

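### The logistic model in Protocol 6.11 adjusts for number of embryos transferred, which is settled after randomisation, so it need not estimate the total effect of GERI+; its role also differs between sections

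*Protocol*

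**What the plan says.** **Covariates.** Protocol 6.11 names smoking status, age, gestational history, COS strategy and embryo culture media, then continues that "luteal phase support, number of embryos transferred and site locations are potential confounding factors in this study". It adds: "Multivariate logistic analysis will be performed with these factors in the model as covariates when testing the primary endpoint".

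**Role of the model.** Protocol 8.4.2 tests the primary hypothesis with a CMH test adjusted for the stratification factors (site and age group). It then says: "As sensitivity analysis, a logistic regression model with confounding factors and stratification factors as covariates will be performed". Model details are left to the SAP.

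**Timing and blinding.** Under Protocol 6.7, subjects are randomised straight after the Day 1 fertilisation check. Transfer is on Day 3 (6.8). Embryologists and clinicians are not blinded (6.6). On how many embryos to transfer, 6.8 says "there is no restriction on the number of embryos to be transferred", with single transfer recommended.

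**Objective.** Protocol 5.1 aims at the overall clinical value of GERI+ as an integrated culture and assessment system.

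**SAP.** Section 7 says the protocol's methods were adopted without change. It then excludes statistical comparison between groups and confidence intervals, and adds: "No regression models will be constructed in this study".

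**The concern.** A confounder of a randomised comparison has to exist before allocation. Number of embryos transferred does not. It is fixed two days later by people who know the arm and, in the GERI+ arm, have the EEVA result in front of them. It may therefore lie on the path from allocation to pregnancy. The objective calls for the total effect of using the system. A model that holds transfer number fixed answers a different question whenever the arms differ in that number, and a reader could take a gap between its odds ratio and the CMH odds ratio as evidence about robustness when it is not.

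The wording adds a second difficulty. Section 6.11 ties the model to testing the primary endpoint, while 8.4.2 assigns that test to CMH. The SAP, which was meant to settle the details, supplies no covariate list. If a model is reinstated, 6.11 is the only list available.

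**Working it through.** **1. The plan's own figure.** Protocol 8.1 states "a two-sided test with an alpha level of 0.05 needs 623 subjects per group to reach a power of 80" per cent, from an "expected clinical pregnancy rate of 30" per cent in control and "a 25% relative increase of clinical pregnancy rate in the experimental group". So the rates are 0.30 and 0.30 × 1.25 = 0.375. The two-proportion formula with pooled variance and no continuity correction gives 623 per group. 623 / 0.9 = 692.2, rounded up to 693, and 2 × 693 = 1,386. The stated size reproduces. The target odds ratio is (0.375/0.625) / (0.30/0.70) = 1.40.

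**2. Order of events.** Randomisation is on Day 1 (6.7) and transfer on Day 3 (6.8), with no limit on number (6.8) and staff unblinded (6.6). Number transferred is therefore a post-randomisation variable that allocation could affect. Nothing in the documents says that it will.

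**3. What adjustment could do.** The documents give no transfer shares and no pregnancy rates by number transferred. The following inputs are *assumptions*: in control, 22% pregnancy with one embryo and 38% with two, half receiving each, so 0.5 × 22% + 0.5 × 38% = 30%. The odds ratio for two versus one is (0.38/0.62) / (0.22/0.78) = 2.17, taken as equal in both arms.

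Model: logit P = b0 + bA × arm + bM × (two embryos). With d the GERI+ share receiving two, bA is solved so that the overall GERI+ rate stays at 37.5%:

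(1 − d) × expit(b0 + bA) + d × expit(b0 + bM + bA) = 0.375.

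The adjusted odds ratio is exp(bA). Example for d = 0.30: the GERI+ rates are 31.94% and 50.48%; 0.7 × 31.94 + 0.3 × 50.48 = 37.5; and (0.3194/0.6806) / (0.22/0.78) = 1.66. The p-values use expected counts at 693 per arm.

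| Two-embryo share, GERI+ vs control | Adjusted OR, rates 37.5% vs 30% (unadjusted 1.40, p = 0.003) | Adjusted OR, rates 30% vs 30% (unadjusted 1.00) |
|---|---|---|
| 30% vs 50% | 1.66 (p < 0.001) | 1.18 (p = 0.18) |
| 45% vs 50% | 1.47 | 1.04 |
| 50% vs 50% | 1.42 (p = 0.003) | 1.00 |
| 55% vs 50% | 1.36 | 0.96 |
| 70% vs 50% | 1.21 (p = 0.10) | 0.86 |

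With an equal mix, the step from 1.40 to 1.42 is only the usual difference between a conditional and a marginal odds ratio.

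**4. Sensitivity to the assumptions.** A second set takes 40% double transfer in control, 20% to 60% in GERI+, and an odds ratio of 1.5 to 2.0 for two versus one. The adjusted odds ratio then runs from 1.23 to 1.63 against 1.40, with power from 38% to 97% at 623 per arm. With equal shares it is 1.40 to 1.41. Adding an unmeasured prognosis factor (odds ratio 3 for pregnancy, poorer prognosis leading to more double transfers) narrows the range to 1.30 to 1.51. In that case the adjusted value is neither the total effect nor the effect at a fixed number: with 20% vs 40% and an odds ratio of 2.0, these are 1.51 adjusted, 1.40 total and 1.64 at a fixed number.

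**5. The three statements of the model's role.** 6.11: used when the primary endpoint is tested. 8.4.2: sensitivity analysis beside a primary CMH test. SAP 7: no model, and no CMH comparison either, under a heading sentence that reports no change. These cannot all hold.

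**The case against.** The strongest reply is that the model will not be run. Protocol 8.4.2 defers its details to the SAP, and SAP 7 excludes regression explicitly. Because SAP 7 also excludes comparisons between groups, there would be no CMH result for the model to contradict. This stands as a limit on how much the point matters today. It does not repair the protocol, because the same SAP section says nothing has changed and offers no replacement covariate list.

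Second, even under the protocol the model is a sensitivity analysis, and 6.11 can be read as loose wording consistent with that. This also stands: the primary CMH test is not affected.

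Third, 6.8 uses EEVA to decide which embryos to transfer, not how many, and recommends single transfer without distinction of arm. The mix may well be similar, in which case adjustment does no material harm. A reader might infer that the adjusted estimate is necessarily biased. The documents do not support that. It depends on whether allocation changes the number transferred, which is unknown. Without an unmeasured common cause, the adjusted odds ratio is a sound estimate of a different quantity, the effect at a fixed number transferred.

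Fourth, a reader might infer that luteal phase support is also chosen after randomisation, because Protocol 7.4 records it at the hCG visit. Time of recording is not time of decision. SAP 13 classifies luteal support by ovulation trigger, which precedes randomisation, and Protocol 9.1 says therapeutic strategy is decided in advance. No decision date is given, so the objection to it as a covariate is not established.

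**Conclusion.** The point holds for number of embryos transferred and for the model's inconsistent role. It is a should-fix matter of specification in a sensitivity analysis, and it has consequences only if the model is run. The order of events, the blinding and the absence of a limit come straight from the protocol. The size does not: every odds ratio other than 1.40 rests on assumed transfer shares and assumed pregnancy rates by number transferred. Under those assumptions the departure is large for 20-point imbalances (1.21 to 1.66), modest for 5-point imbalances (1.36 to 1.47) and negligible for none (about 1.42). Because the mix cannot be known in advance, this covariate should not be pre-specified in a model meant to support a total-effect claim. The loss of the CMH test in SAP 7 is the larger problem for the trial, but it is a separate one.

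**What to change.** - In Protocol 6.11 and 8.4.2, remove number of embryos transferred from the model. Limit covariates to factors fixed before randomisation: site, age stratum, smoking, gestational history, COS strategy and the site's routine culture medium.
- Keep luteal support only in a form shown to be fixed before randomisation, such as trigger type. Otherwise omit it.
- State in 6.11, as in 8.4.2, that the stratified CMH test is primary and the model is a sensitivity analysis.
- Align SAP 7: restore the CMH test with its odds ratio and confidence interval and, if a model is run, give the restricted covariate list there. Otherwise, declare its removal as a change from the protocol.

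The cost is wording in the two documents. No patients are added, the 1,386 stands, and the CMH test loses no power. No new eCRF field is needed, and nothing here restricts how many embryos are transferred. SAP 13 and 14.3.6 already tabulate luteal support and number transferred by arm, so any imbalance will be visible.
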